### **5 Sample Size Justification**

This study sample size was established to provide adequate precision on the mean subsidence estimate at 2 years for each surgical approach. A common standard deviation of 0.2 mm is anticipated. Based upon this standard deviation and a sample size of N=30, a

2-sided 95% confidence interval for each respective surgical approach is anticipated to have a margin of error equal to approximately  $2SE = 2 * \frac{SD}{\sqrt{N}} = 2 * \frac{0.2}{\sqrt{30}} = 0.073mm$ . This margin of error was deemed to be an adequate level of precision by the Sponsor.

## 6 Analyses to be Conducted

### 6.1 General Conventions

All statistical analyses will be performed using SAS® Version 9.4 or higher, unless otherwise noted. Standard descriptive summaries for continuous data include the number of subjects with non-missing observations (n), mean, standard deviation (SD), median, minimum, and maximum values. For categorical data, the count and percentage will be provided. Percentages will be based on the number of subjects without missing data. If exploratory tests of hypotheses are performed, t-tests will be performed for continuous variables, and Fishers' Exact Test will be performed for categorical variables. Baseline for the RSA analysis is 6 weeks with the exception of the exploratory analysis of the subset where RSA data is available prior to discharge. Baseline for the Forgotten Joint Score and for linear head penetration is also 6 weeks. Baseline for all other endpoints is the pre-operative measurements collected before surgery. Unless specifically stated otherwise, all endpoints will be analyzed by surgical approach and overall, pooling all surgical approaches.

### 6.2 Disposition of Study Subjects

Counts of the following categories of subjects by surgical approach and in total will be provided: All Enrolled dataset, Safety, major inclusion/exclusion protocol violations, Per Prototol, non inclusion/exclusion major protocol violations, deaths, withdrawals, study completion, ongoing in the study.

A subject accounting table using the Safety set will also be provided to account for the following at each follow-up interval:

- Treated: the count of subjects treated. This should not vary per visit;
- Not Yet Due: the count of subjects who do not have an evaluation at the visit and who, based on date of surgery and date of data extract, are not yet in-window for the visit;
- Theoretical Due: the count of subjects treated and not counted in Not Yet Due.
- Death: the count of theoretical subjects who died after the start of the window and who do not have data at the visit;
- Revision: the count of subject theoretically due, without data at the visit, who were revised. Revisions will be identified through consensus between Medical Affairs and the clinical study team using the data from the AE and study completion CRFs;
- Not Yet Overdue: count of theoretical subjects within the evaluation time window. Do not count subjects who have data at the visit or subjects who are counted in Death or Revision;
- Expected Due: the count of subjects theoretically due who are not counted in Death, Revision, Not Yet Overdue;
- Actual data on file (records with a date): the count of Expected subjects with a record with a date for each of the following endpoints: RSA measured subsidence, cup positioning (6 Weeks only), Harris Hip, HOOS Jr., Forgotten Joint Score, and Linear Head Penetration. A count of subjects with a record with a date in any of the listed endpoints will also be provided and a follow-up rate will be calculated using the number of Expected subjects in the interval as denominator;
- Scorable data: the count of Expected subjects with a record with a date and where the endpoint was scorable/non-missing for the following endpoints: RSA measured subsidence, cup positioning (6 Weeks only), Harris Hip, HOOS Jr., Forgotten Joint Score, and Linear Head Penetration. A count of subjects with a record with a date of all of the listed scorable endpoints will also be provided and a follow-up rate (complete data) will be calculated using the number of Expected subjects in the interval as denominator.

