## 2 Interval Windows

The study includes the following periods: Pre-op, Operative, Prior to Discharge, 6 Weeks, 3 Months, 6 Months, 1 Year, 2 Years. Intervals related to each are shown in Table 3, below.

Table 3 Interval Windows for Non-Radiographic Study Visits

Visit	Minimum Day	Maximum Day	Midpoint Day
Pre-Op*	-90	0	
Operative	0	0	0
Prior to Discharge	1	Discharge	
6 Weeks	28	56	42
3 Months	60	120	90
6 Months	135	225	180
1 Year	275	455	365
2 Years	640	820	730

\* For radiographs Pre-Op study film window is from -270 days to DOS.

Time point specific data collected to satisfy the primary and secondary efficacy-related objectives will be assessed for compliance with these intervals. Only data which can be attributed to the visit intervals in Table 3 will be used in the analysis of primary and secondary endpoints. This visit will be hereafter referred to as the Analysis Visit and the originally recorded visit as the Nominal Visit. If multiple measurements fall into the pre-

operative window, or into the ‘Prior to Discharge’ post-operative window, the result collected most proximate to surgery will be utilized. For all post-operative visits after the ‘Prior to Discharge’ visit, if multiple measurements fall into the window then the last value within the window will be utilized for analysis.

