## **6.6 Primary Endpoint and Associated Hypotheses**

### RSA Measured Subsidence at 2 years

The primary endpoint of RSA measured subsidence (Y translation from week 6 in mm, also known as superior cup migration) results in the 2-year visit window will be summarized on the subset of subjects in the Per Protocol Analysis Set (primary analysis) who have 6 week and 2 year data for the analysis. The analysis will also be conducted on the subset of subjects in the Safety Analysis Set (supportive analysis) who have 6 week and 2 year data for the analysis. Standard continuous summaries will be provided along with 95% confidence intervals. These summaries will be provided for each surgical approach, as well as combined.

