## **6.10 Plans for Interim Analysis**

There are no formal interim analyses that are designed to potentially stop or change the study design. A planned interim summary analysis will take place after all subjects have completed the 1 year visit in order to give product development an understanding of acetabular cup subsidence that might be expected for future product development purposes. There is no intention to utilize this interim analysis as a means to justify stopping the study early.

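### SAP 6.2 accounting table: Death has no closing date and Revision no date, so Expected Due keeps early deaths and drops subjects who died or were revised after a missed visit

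*SAP*

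**What the plan says.** SAP 6.2 plans an accounting table on the Safety set, with one column per follow-up interval. The rows that matter are these:

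- Not Yet Due depends on whether the subject has an evaluation, on the surgery date and on the extract date.
- Theoretical Due is everyone treated apart from those in Not Yet Due.
- Deaths are handled by this line: "Death: the count of theoretical subjects who died after the start of the window and who do not have data at the visit". It has an opening date and no closing date.
- Revisions are handled by this one: "Revision: the count of subject theoretically due, without data at the visit, who were revised". It has no date of either kind.
- Not Yet Overdue holds subjects still inside the window who lack data and have not been placed in one of the two rows above.
- The denominator is what remains: "Expected Due: the count of subjects theoretically due who are not counted in Death, Revision, Not Yet Overdue".

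Expected Due is then used twice. For subjects with any dated record, "a follow-up rate will be calculated using the number of Expected subjects in the interval as denominator", and the rate for complete, scorable data uses the same denominator.

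The windows are in Table 3 of SAP section 2. Protocol 9.10 describes the same table by row name only. It includes deaths and a withdrawn row, and gives no timing rule for either. The SAP table has no withdrawn row.

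**The concern.** A subject is expected at a visit if treated, alive and unrevised through that visit's window. To find such subjects, deaths and revisions must be counted cumulatively from surgery to the end of the window. The Death row does something else. It starts counting when the window opens and never stops. The Revision row has neither a start nor a stop.

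**Early deaths stay in.** Theoretical Due ignores vital status, so a subject who died before a window opened is still theoretically due. That subject is not in Death. Once the window has closed the subject is not in Not Yet Overdue either, and so is counted as expected and lost.

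**Late events drop out.** A subject alive through the 6-month window who missed that visit and died on day 700 did die after the window started. The Death row therefore removes this subject from the 6-month denominator, and a real missed visit disappears. A revision on day 700 has the same effect.

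The SAP plans no imputation (6.11) and no sensitivity analyses (6.13), so these two rates are its main visit-level display of completeness. They should count the right people.

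**Working it through.** The documents print no figure for this table, so there is nothing to reproduce. The check applies the rows as written to assumed subjects. It then repeats the count with both events dated on or before the last day of the window.

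**Inputs.** Windows from SAP Table 3, in days: 6 weeks 28–56, 3 months 60–120, 6 months 135–225, 1 year 275–455, 2 years 640–820. Planned size from the protocol summary: 90, with 30 per approach. All death, revision and missed-visit counts below are assumed.

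**Days on which a death is not counted**, (window start − 1) / window end:

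| Visit | Days missed | Share |
|---|---|---|
| 6 weeks | 27/56 | 48.2% |
| 3 months | 59/120 | 49.2% |
| 6 months | 134/225 | 59.6% |
| 1 year | 274/455 | 60.2% |
| 2 years | 639/820 | 77.9% |

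These are shares of calendar days, not of deaths. If the start day itself is also excluded, the 2-year figure is 640/820 = 78.0%.

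**One early death**, rate = subjects with data / Expected Due, window closed:

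| Treated | With data | As written | Corrected | Difference (points) |
|---|---|---|---|---|
| 90 | 89 | 89/90 = 98.9% | 89/89 = 100% | 1.1 too low |
| 90 | 72 | 72/90 = 80.0% | 72/89 = 80.9% | 0.9 too low |
| 30 | 29 | 29/30 = 96.7% | 29/29 = 100% | 3.3 too low |
| 30 | 24 | 24/30 = 80.0% | 24/29 = 82.8% | 2.8 too low |

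With 1, 2, 3 or 5 deaths before day 640 and everyone else seen, the 2-year rate among 90 cannot exceed 98.9, 97.8, 96.7 or 94.4%. It should be 100%.

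**One late death or revision after a missed 6-month visit:**

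| Treated | With data | As written | Corrected | Difference (points) |
|---|---|---|---|---|
| 90 | 86 | 86/89 = 96.6% | 86/90 = 95.6% | 1.1 too high |
| 30 | 28 | 28/29 = 96.6% | 28/30 = 93.3% | 3.2 too high |

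**Both errors in one cohort.** Take 90 treated subjects, of whom 85 are complete. The other five are:

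- A died on day 200.
- B missed 3 months and died on day 300.
- C died on day 700.
- D missed 3 months and was revised on day 500.
- E was revised on day 100.

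Each has data at every other visit before the event.

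| Visit | With data | Expected Due as written | Rate | Expected Due corrected | Rate |
|---|---|---|---|---|---|
| 3 months | 87 | 87 | 100.0% | 89 | 97.8% |
| 6 months | 88 | 88 | 100.0% | 88 | 100.0% |
| 1 year | 87 | 88 | 98.9% | 87 | 100.0% |
| 2 years | 85 | 87 | 97.7% | 85 | 100.0% |

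As written, the 3-month column hides two missed visits (B and D), and the 2-year column shows two losses that are deaths (A and B). B is in Death at 3 months, while still alive, and again at 1 year, yet is expected at 2 years.

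**The errors can cancel.** At 6 months, take 90 treated: one died on day 100, four missed the visit alive (one of whom died on day 700), and 85 have data. Both rules give 85/89 = 95.5%. As written, the day-100 death is kept and the day-700 death is removed, so the total looks right with the wrong subject excluded.

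**Extract timing.** SAP 6.10 says "A planned interim summary analysis will take place after all subjects have completed the 1 year visit". At that extract the early-death error affects visits whose windows have closed. While a window is open, an early death falls into Not Yet Overdue instead. It reaches the 2-year Expected Due only after that window closes. At 2 years the late-event error has little room, because Protocol 7.4 ends adverse event reporting with study participation.

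**The case against.** The strongest reply is that this touches one descriptive table. No threshold or decision uses the follow-up rate, and the sample size has no attrition term. Deaths are also counted overall in SAP 6.2 and in the safety summary in 6.9. All of that stands and sets the severity.

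A second reply is that the rows are introduced as an account for each follow-up interval, so a programmer might read the Death row as limited to events inside the interval. That reading would remove the late-death example. It would not remove early deaths from Expected Due, and it does not date the Revision row.

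Third, SAP section 10 places the table shells in a separate file that was not available for this review. The shells may carry a date rule, so how the table would actually be programmed is not known. The definitions in the SAP text are still wrong as they stand.

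Fourth, the size can be overstated. The late-event error needs a missed visit followed by a death or revision in the same subject. For a revision before or during the window, the undated row already gives the right answer. The figures for 30 apply only if this table is split by approach, which SAP 6.2 does not state for it. The total of 90 is a plan, since Protocol 6.2 keeps any extra subjects. These limits are accepted.

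Finally, whether withdrawn subjects stay in the denominator is a matter of convention, and the SAP's choice may stand. Keeping early deaths is not a consistent convention here: a subject revised on day 100 is removed at 2 years, while one who died on day 100 is not.

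**Conclusion.** The concern holds. As written, SAP 6.2 gives a wrong denominator for both follow-up rates whenever a subject dies before a window that has since closed, or dies or is revised after missing a visit. The first case understates a later visit's rate, and the second overstates an earlier one. The size is about 1 point per affected subject with 90 treated, about 3 points with 30 if the table is split by approach, and zero if no such event occurs. The documents give no event rates, so the number of affected subjects is unknown.

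The point is minor. The primary summary is restricted to subjects "who have 6 week and 2 year data for the analysis", so the mean subsidence and its confidence interval are unaffected.

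**What to change.** In SAP 6.2:

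1. Define Death as theoretically due subjects without data at the visit who died on or before the last day of that visit's window, counted cumulatively from surgery.
2. Give Revision the same end-of-window cut-off.
3. State that each subject is counted in one row only, for example Death and then Revision. Protocol 8.1 lists both as reasons for discontinuation. The existing wording of Expected Due already prevents double subtraction and should be kept; the precedence rule makes the displayed rows add up.
4. Add a cumulative Withdrawn row per interval, for display only, to match Protocol 9.10. Exclude subjects already in Death or Revision.

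With change 1, an early death whose window is still open at the extract moves from Not Yet Overdue to Death under the existing exclusion, so that row needs no edit. Check the table shells for consistency.

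The cost is two definition lines, one precedence sentence and one display row. No new data are needed and no endpoint analysis changes.

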### **6.3 Demographic and Baseline Characteristics**

Descriptive statistics will be summarized for the subjects in the Safety Analysis Population and for the subjects in the Per Protocol population (both in total and by surgical approach):

- Age at consent (in years);
- Sex;
- Child's bearing potential if Sex is Female;
- Height (cm);
- Weight (kg);
- BMI ( $\text{kg}/\text{m}^2$ );
- Clinical ( $30 \leq \text{BMI} < 40$ ) & morbid obesity ( $\text{BMI} \geq 40$ );
- Primary diagnosis;

### **6.4 Operative details**

Operative details will be summarized for the subjects in the Safety Analysis Population and for the subjects in the Per Protocol population (both in total and by surgical approach):

- ASA Risk;
- Surgical time (Duration) (min);
- Anesthesia time (Duration) (min);
- Surgical approach;
- Use of wires/cables;
- Use of screws. Additional details regarding the use of screws will be provided in a listing;
- Acetabular bone graft;
- Acetabular bone class;
- Acetabular osteophytes removed;
- Femoral bone graft;
- Femoral bone class proximal;

- Femoral bone class distal;
- DORR class.

## **6.5 Device Deficiencies and Protocol Deviations**

Listings of device deficiencies and protocol deviations will be provided.

## **6.6 Primary Endpoint and Associated Hypotheses**

### RSA Measured Subsidence at 2 years

The primary endpoint of RSA measured subsidence (Y translation from week 6 in mm, also known as superior cup migration) results in the 2-year visit window will be summarized on the subset of subjects in the Per Protocol Analysis Set (primary analysis) who have 6 week and 2 year data for the analysis. The analysis will also be conducted on the subset of subjects in the Safety Analysis Set (supportive analysis) who have 6 week and 2 year data for the analysis. Standard continuous summaries will be provided along with 95% confidence intervals. These summaries will be provided for each surgical approach, as well as combined.

## **6.7 Secondary Endpoints**

### 6.7.1 RSA Measured Subsidence and maximal total point motion at 3 months, 6 months, 1 year, and 2 years

X, Y, and Z translations from week 6 in mm and A, Y, and Z rotations in degrees, and maximal total point motion in mm will be summarized at the 3 month, 6 month, 1 year, and 2 years visit windows using the Per Protocol Analysis Set and the Safety Set. Standard continuous summaries will be provided along with 95% confidence intervals. These summaries will be provided for each surgical approach, as well as combined.

### 6.7.2 Cup Positioning at 6 weeks

Inclination and version will be assessed at 6 weeks from the AP radiographs using Martell software. Summaries will be provided using the Per Protocol Analysis Set.

### 6.7.3 Linear head penetration at 6 weeks, 3 months, 6 months, 1 year, and 2 years

Linear head penetration (in mm) is the change in distance between the center of the femoral head and the center of the acetabular shell between the 6-week (baseline) exam and the 3 months, 6 months, 1 year and 2 year exam. The distance between the centers within each visit window will be summarized and the change from baseline will be provided using the Per Protocol Analysis Set.

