## 6.5 3 Month, 6 Month, 1 Year and 2 Year Visits

The subject will have the following health and functional status evaluations:

- Harris Hip Score
- Hip Evaluation
- HOOS Jr.
- Forgotten Joint Score
- Adverse Events (if applicable)
- Radiographs
  - AP Femur
  - Lateral
- RSA Exam (supine position)

The information collected from these visits will be populated on the appropriate eCRFs as indicated in the Time and Events Table (Section 1.1).

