## 6.7 Radiostereometric Analysis (RSA)

The RSA analysis will be the responsibility of the Canadian RSA Network. In summary, model based RSA software (RSAcore, Leiden, Netherlands) will be used for analysis, employing computer-models of the DePuy Synthes implants and inserted beads representing the bone rigid body. A central analysis service will be employed to analyze anonymized radiographs in a standard manner. DePuy Synthes will provide production CAD models as required for this analysis.

Three-dimensional migration measurements will be made of the acetabular shell relative to the bone beads. The 6-week examination will be used as reference against which the 3-month, 6-month, 1-year and 2-year post-operative exams will be compared. Results obtained from the model based RSA software will be changes from the 6-week (baseline) examination and will report the following at 3 months, 6 months, 1 year and 2 years:

- X, Y and Z translation measurements in mm from baseline;
- X, Y and Z rotation measurements in degrees from baseline;
- Maximal total point motion (one measurement in mm of maximal migration).

Three-dimensional migration of the Pinnacle Acetabular Shell shall be determined from the software.

Linear head penetration (in mm) will be performed by examining the change in distance between the center of the femoral head and the center of the acetabular shell between the 6-week (baseline) exam and 1 year and 2 year exam. The femoral head center is determined by fitting a CAD sphere to the articular region of the femoral head (ignoring the trunnion area). The acetabular shell center is determined in a similar manner but also uses the silhouette of the cup face to determine its' centerpoint.

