### 9.6.2 Secondary Endpoints

The secondary endpoints are the following:

- RSA measured subsidence (superior cup migration) at 3 months, 6 months and 1 year.
- Other RSA measurements (X and Z translations in mm, X, Y, and Z rotations in degrees, and maximal total point motion in mm) at all time points
- Linear head penetration at, 1 year and 2 years;
- Harris Hip Score at 6 weeks, 3 months, 6 months, 1 year and 2 years;
- HOOS Jr. at 6 weeks, 3 months, 6 months, 1 year and 2 years;
- Forgotten Joint Score (FJS-12) at 6 weeks, 3 months, 6 months, 1 year and 2 years.

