#### Linear Head Penetration at 1 year and 2 years

Linear head penetration will be assessed at 6 weeks, 1 year and 2 years. Results within each visit window will be summarized and changes from baseline will be provided using the Per Protocol Analysis Set.

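### Linear head penetration has one visit schedule in the protocol and a longer one in the SAP, and the SAP's complete-data rate counts it, and subsidence, at every visit

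*SAP*

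**What the plan says.** **Protocol.** Wherever the protocol gives visits for linear head penetration, they are 1 and 2 years, with 6 weeks as reference.

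- Section 6.7 measures the change in head-to-shell centre distance "between the 6-week (baseline) exam and 1 year and 2 year exam".
- Section 9.6.2 lists "Linear head penetration at, 1 year and 2 years". Section 3.2 and the study summary agree.
- Section 9.12.2 adds the baseline reading: "Linear head penetration will be assessed at 6 weeks, 1 year and 2 years".

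Section 6.7 treats shell migration separately: "The 6-week examination will be used as reference against which the 3-month, 6-month, 1-year and 2-year post-operative exams will be compared". The outputs it lists for those four visits are translations, rotations and maximal total point motion. Penetration is not on that list.

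**SAP.** Sections 1.1.2 and 6.7.3 define penetration as the change "between the 6-week (baseline) exam and the 3 months, 6 months, 1 year and 2 year exam". Section 6.7.3 also summarises the centre-to-centre distance itself in each visit window, and its heading includes 6 weeks.

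SAP 6.2 describes an accounting table for each follow-up interval. Its scorable-data item names six endpoints: RSA subsidence, cup positioning, Harris Hip, HOOS Jr., Forgotten Joint Score and linear head penetration. Cup positioning is restricted to 6 weeks; the others have no visit restriction. The section continues: "A count of subjects with a record with a date of all of the listed scorable endpoints will also be provided", and divides that count by the Expected subjects to give a complete-data follow-up rate.

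**The concern.** Protocol section 9 says the SAP will reflect the protocol and its implemented amendments. On this secondary endpoint it does not, and the SAP neither mentions nor explains the two added visits. The central lab has one document telling it what to read and the programmer has another telling them what to tabulate.

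The mismatch carries into the follow-up table. A rate that requires every listed endpoint to be scorable is only as high as its least available component. If a component is not due at a visit, the rate reports incomplete data where every scheduled item was done. A reader using that table to judge the quality of the RSA series could be misled about the 3- and 6-month visits. At 6 weeks, the table as worded asks for a subsidence value, when the useful figure is how many subjects have a usable reference exam.

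**Working it through.** **1. Schedules side by side**

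| Source | 6 weeks | 3 months | 6 months | 1 year | 2 years |
|---|---|---|---|---|---|
| Protocol 3.2, 9.6.2 | – | no | no | yes | yes |
| Protocol 6.7 | reference | no | no | yes | yes |
| Protocol 9.12.2 | assessed | no | no | yes | yes |
| SAP 1.1.2 | reference | yes | yes | yes | yes |
| SAP 6.7.3 | reference, distance summarised | yes | yes | yes | yes |
| SAP 6.2 (complete-data rate) | no limit | no limit | no limit | no limit | no limit |

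The documents disagree at 3 and 6 months only.

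**2. Could penetration be obtained at 3 and 6 months?** Yes. Protocol 1.1 and 6.5 schedule an RSA exam for every subject at both visits, and Protocol 6.7 sends those exams to central model-based analysis. Penetration comes from fitting models of the head and shell to the exam, and no separate acquisition is described. The images are scheduled; the protocol does not ask for this reading from them.

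**3. Complete-data rate at 3 and 6 months.** The plan gives no completeness figure to reproduce. From the SAP 6.2 rule:

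rate = p_other × p_LHP

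Here p_other is the share of Expected subjects with all other due endpoints scorable, and p_LHP is the share of those with penetration read. Assumptions: 90 Expected subjects (the planned enrolment, with no deaths or revisions) and a p_other of 80%, 90% or 100%. SAP 6.11 rules out imputation, so an unread value stays missing.

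| p_other | p_LHP = 0 | p_LHP = 0.5 | p_LHP = 0.9 | p_LHP = 1 |
|---|---|---|---|---|
| 0.80 | 0% (0) | 40% (36) | 72% (64.8) | 80% (72) |
| 0.90 | 0% (0) | 45% (40.5) | 81% (72.9) | 90% (81) |
| 1.00 | 0% (0) | 50% (45) | 90% (81) | 100% (90) |

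Subjects are in brackets; for example, 90 × 0.90 × 0.5 = 40.5. The first column is the result if the lab keeps to Protocol 6.7. The last is the result if it reads penetration from every 3- and 6-month exam. The range is therefore 0% up to p_other.

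**4. The 6-week row.**

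- *Subsidence.* SAP 6.6 defines it as Y translation from week 6, and Protocol 6.7 reports it from 3 months on. In the main analysis the 6-week value is the exam compared with itself: zero by construction, or undefined.
- *Penetration.* The change has the same problem, but the centre-to-centre distance is a real 6-week value under Protocol 9.12.2 and SAP 6.7.3.
- *Exception.* SAP 1.1.3, 6.1 and 6.8 allow a different baseline for subjects with a pre-discharge RSA exam. Those subjects can have a 6-week subsidence value in an exploratory analysis.

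**5. What is not touched.** The stated precision, 2 × 0.2/√30 = 0.073 mm, concerns 2-year subsidence and does not involve penetration or the accounting table.

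**The case against.** The strongest reply is that the SAP's longer schedule looks deliberate: it appears in two sections, and the exams it needs are already taken. A reader might infer from the mismatch that the 3- and 6-month results will be empty and the rate will be 0%. The documents do not support that as a certainty. It follows only if the lab reads no penetration at those visits, so it is the worst case. This part of the reply stands. It does not remove the contradiction, because the protocol's instruction to the lab still omits those visits, and a lab that followed it would produce exactly that worst case.

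A reader might also infer that the rate is 0 of 90 at 6 weeks, so that three of the five follow-up visits fail. That does not stand. A 6-week centre distance exists, some subjects may have a 6-week subsidence value in the pre-discharge subset, and a programmer might count the reference exam as scorable.

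Other mitigations are fair. SAP 6.2 also reports counts for each endpoint and a second rate based on any listed endpoint, so an attentive reader could trace a shortfall to penetration. The table shells are in a separate document (SAP 10) that was not available, and they may blank cells that are not due. The Per Protocol count depends on a 6-week RSA exam, but it also requires a later exam and no major eligibility violation. It is therefore not a count of usable reference exams.

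**Conclusion.** The point holds in conditional form. The protocol and SAP give linear head penetration different schedules at 3 and 6 months, and SAP 6.2 counts penetration and subsidence in the complete-data rate without saying when each is due. At 3 and 6 months that rate lies between 0% and the completeness of the other endpoints, depending on whether the lab follows Protocol 6.7 or also reads the existing exams. The subject counts rest on an assumed 90 Expected subjects and assumed completeness; the 0% floor depends on neither. At 6 weeks the defect is narrower: main-analysis subsidence has no meaningful value there, so the row does not state directly how many usable reference exams exist.

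The stakes are modest: one descriptive secondary endpoint and one accounting table. There are no hypothesis tests. It is still worth correcting, because two stated rules followed together would produce a wrong follow-up figure.

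**What to change.** Give penetration one schedule, by either route:

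- amend Protocol 3.2, 6.7, 9.6.2 and 9.12.2 (and the study summary) so that the lab also reads penetration from the 3- and 6-month RSA exams already taken; or
- limit SAP 1.1.2 and 6.7.3 to the 6-week baseline, 1 year and 2 years.

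The first costs a short amendment and some extra reading by the central lab, with no added exam for subjects. The second costs SAP wording only.

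Under either route, tag each endpoint in SAP 6.2 with the visits at which it is due, as is already done for cup positioning: subsidence from 3 months, penetration change at its agreed visits, and a usable reference RSA exam at 6 weeks in place of both. Define complete data at a visit as all endpoints due at that visit being scorable, and bring the table shells into line.
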